8. RESEARCH QUESTION AND OBJECTIVES

Exploratory Objectives	Exploratory Endpoints
• To estimate incidence rates for hospitalised CAP and SP+CAP (both overall and radiologically confirmed) in the surveillance region within the limitations of the expected under ascertainment of hospital-based screening process and current diagnostic testing.	 Number of CAP events identified by screening log divided by number of persons ≥60 years in surveillance region.
• To compare the effectiveness of PPV23 to that of PCV13 in preventing cases of hospitalised VT- pneumococcal CAP among adults aged ≥60 years using a test-negative study design, overall and among immunocompetent persons only.	• Final adjusted VE point estimate for PPV23 subtracted from final adjusted VE subtracted for PCV13, overall and among immunocompetent persons only.
• To compare pneumococcal serotype results from high-quality respiratory specimens (standard –of care), UAD1/2 (study procedure), and saliva specimens taken for carriage testing (study procedure).	 Percent agreement in serotype results between specimen types for events that have both types available. (Three comparisons: 1. high-quality respiratory culture [standard –of care specimen] versus UAD1/2; 2. UAD1/2 versus saliva carriage sample; 3. High-quality respiratory culture versus saliva carriage sample).
• To estimate incidence rates for hospitalised CAP among adults aged ≥60 years with underlying at-risk and high-risk medical conditions, in aggregate and for individual risk conditions within the limitations of the expected under ascertainment of hospital- based screening process and current diagnostic testing.	 Number of CAP events identified by screening log multiplied by the proportion of CAP subjects with specific risk condition(s) divided by the estimated number of persons ≥60 ears in surveillance region with the same specific risk condition(s), in aggregate for at-risk and high-risk conditions and for individual risk groups if the size of risk group is adequate for a stable estimate.

Additional COVID-19 Exploratory Objectives	Additional COVID-19 Exploratory Endpoints

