	Population of 60 years and older	Percentage of people of 60 years and older
Hospital Universitario de Móstoles, Móstoles	35,106	25.5%
Hospital Universitario Rey Juan Carlos, Móstoles		
Hospital Universitario Fundación Alcorcón, Alcorcón	46,802	27,1%

Note: Hospital Universitario de Móstoles and Hospital Universitario Rey Juan Carlos have the same geographic catchment area.

Figure 1. Map of Study Locality

PCV13 effectiveness against hospitalised VT-Pneumococcal CAP will be assessed using a TND, which is a modified case-control study. In the TND, researchers are not aware of participants' case/control status at recruitment, but later classify the participants into cases or controls according to the test results. Cases are participants testing positive for PCV13 serotypes by any method, including routine culture from blood, high-quality respiratory culture, or serotype-specific UAD1. For the analysis, PCV13 serotypes will be defined as all serotypes contained in PCV13 (ie, 1, 3, 4, 5, 6A, 6B, 7F, 9V, 14, 18C, 19A, 19F, 23F).

PFIZER CONFIDENTIAL CT45-GSOP-RF152.0 Low-Interventional Study Protocol Template 05-Dec-2019 Page 29 of 70

Controls are hospitalised patients with pneumonia meeting the inclusion and exclusion criteria but testing negative for PCV13-type infection or related serotypes. Vaccine effectiveness is calculated as follows:

 $VE = (1 - vaccination odds ratio) \times 100\%$.

TND validity is predicated on the core assumption that the intervention (vaccine) has no effect on other non-targeted aetiologies resulting in similar illness/disease incidence in the vaccinated and unvaccinated. Compared with conventional case-control or cohort designs, the TND is less susceptible to bias caused by differences in health-care- seeking behaviour among cases and controls and the use of non-specific outcome measurements. However, TND is prone to selection bias, residual confounding due to healthy vaccinee effects and risk-based vaccination strategies, bias due to indirect effects of the vaccine, and misclassification of false-negative cases and controls, these concerns will be addressed, discussed and acknowledged as limitations of the study.

Further, statistical adjustments will be undertaken to control for confounding (eg, propensity score matching).

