study hospitals. Patients with pneumonia who are not enrolled will be recorded on the screening log, which will be the basis of the count of CAP events for incidence estimates. Where appropriate population-based denominators are available, incidence rates for at-risk and high-risk conditions will be generated in aggregate and by condition for more frequent conditions. Nevertheless, incidence estimates will be conservative, given established multiple risks for under ascertainment of pneumonia events in studies in this setting (for example, due to misdiagnosis, chest X-ray [CXR] false negative, or hospitalisation on a different inpatient ward). Non-residents of the hospitals' geographic catchment area will be excluded from incidence estimations.

COVID-19 and pneumococcal infection. The World Health Organization declared COVID-19 a pandemic during the finalization of this protocol (March 11, 2020). On this basis, additional exploratory objectives related to the relationship between COVID-19 and pneumococcal infection were added. If COVID-19 continues to occur at a sufficient frequency in the surveillance region during enrolment to allow for a meaningful analysis, these objectives will be pursued using COVID-19 infection status based on standard –of care testing. Further, if a high incidence of COVID-19 infections is burdening the hospitals at the anticipated time of study start or at some point during study enrolment period, enrolment will be delayed or halted to allow involved staff to focus on COVID-19 clinical care.

This study will prospectively enroll adults, aged 60 years and over, who are hospitalised with CAP in one of the study hospitals: Hospital Universitario de Móstoles, Hospital Universitario Fundación de Alcorcón, and Hospital Rey Juan Carlos de Móstoles (as of February 2022, additional sites may be included at a later date).

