12.4.2. CAP Incidence Rate

Incidence rates (IR) per 100,000 inhabitants of the study age group will be calculated with their respective 95% confidence intervals.

Numerator: The numerator will include all CAP events – both involving study subjects and other unconsented patients captured on screening log as residents of the hospitals' geographical catchment area. Frequent retrospective review of admissions assigned pneumonia ICD discharge codes will be undertaken monthly to ensure no CAP events are missed from the screening log. Efforts will also be made to assess how many persons from the district were hospitalised for pneumonia outside of the surveillance region.

For SP+CAP, the proportion of CAP events among study subjects with pneumococcus identified by any means, will be multiplied by the calculated CAP incidence rate. For radiologically confirmed CAP, the proportion of CAP events among study subjects that is radiologically confirmed will be multiplied by the calculated CAP incidence rate. Other more complex adjustment processes will also be explored if there is adequate detail captured in the screening log, such as calculation the proportion with pneumococal infection within specific risk/age strata or multiple imputation.

Denominator: Annual population data over 60 years old and estimated person-years data for this age group will be obtained from INE (National Statistical Institute). To determine denominators (catchment area), calculations will be made based on the following parameters: age-specific strata of the total population in the region of Madrid; age-specific strata of total hospital discharges in the region of Madrid; age-specific strata of hospital discharges of the Móstoles (2 hospitals) and Alcorcón (1 hospital). Catchment area is calculated as the proportion of the Móstoles and Alcorcón hospital discharges compared to total hospital discharges in the region of Madrid. These percentages are then applied to the total population of the region of Madrid and hence, catchment population in the Móstoles and Alcorcón hospitals by age group are estimated. If population denominators for adults aged ≥ 60 years are available for underlying at-risk and high-risk medical conditions, incidence will be calculated specifically for these risk groups in aggregate and for individual risk conditions that are of sufficient size as outlined in the SAP.

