## Cases and controls for VE against PPV23

The cases are the patients with CAP in whom any one of the 23 serotypes in PPV23: 1, 2, 3, 4, 5, 6B, 7F, 8, 9N, 9V, 10A, 11A, 12F, 14, 15B, 17F, 18C, 19A, 19F, 20, 22F, 23F, and 33F is identified.

The controls are the patients with NVT episode of CAP. Participants having both VT and NVT serotypes will not be included in the controls.

 Percent agreement in serotype results between specimen types for events that have both types available (Three comparisons: 1. high-quality respiratory culture [standard-of-care specimen] versus UAD1/2; 2. UAD1/2 versus saliva carriage sample; 3. High-quality respiratory culture versus saliva carriage sample).

This analysis will include the participants who have at least two of the following with a valid test result: high quality respiratory culture, UAD1/2, or saliva samples.

• Number of CAP events identified by screening log multiplied by the proportion of CAP subjects with specific risk condition(s) divided by the estimated number of persons ≥60 years residents in the hospitals' catchement area with the same specific risk condition(s), in aggregate for at-risk and high-risk conditions and for individual risk groups if the size of risk group is adequate for a stable estimate.

DMB02-GSOP-RF02 5.0 Statistical Analysis Plan Template 05-Dec-2019
PFIZER CONFIDENTIAL
Page 12
TMF Doc ID: 98.03

The denominator will be the population living in the hospitals' catchment area with the risk condition(s), which will be obtained from local source(s) depending on availability.

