# 6.3.4.1. Exploratory Endpoint 4 - Main Analysis

The incidence rate among the high-risk population  $(IR_{hr})$  will be calculated as

$$IR_{hr} = \frac{(\textit{no.of cases in the high risk category} \div \textit{no.of years of surveillance})}{\textit{total high risk population in the hospitals' geographical catchment area}} \times 100,000$$

The incidence rate among the at-risk population  $(IR_{ar})$  will be calculated as

$$IR_{ar} = \frac{(no.\,of\,\,cases\,\,in\,\,the\,\,at\,\,risk\,\,category\,\div\,no.\,of\,\,years\,\,of\,\,surveillance)}{total\,\,at\,\,risk\,\,population\,\,in\,\,the\,\,hospitals'\,geographical\,\,catchment\,\,\,area} \times 100,000$$

The no. of years of surveillance will be calculated as

(date of last participant first visit – date of the start of surveillance period +1)/365.25

If the data do not provide complete years (e.g. 1 year, 2 years, etc.), then the no. of years of surveillance will be adjusted for seasonality, if the data on seasonality are available for the sites.

Note that we will apply the proportion of CAP events in a specific risk group among enrolled participants to account for the number of CAP events in specific risk group among the unenrolled patients. The risk population will be obtained by multiplying the frequency of a given risk factor obtained from other sources (e.g., UAD control subjects or real-world data analyses) by

DMB02-GSOP-RF02 5.0 Statistical Analysis Plan Template 05-Dec-2019
PFIZER CONFIDENTIAL
Page 38
TMF Doc ID: 98.03

denominator counts for that age group from local government sources. This analysis will be performed if such data are made available.

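### SAP 6.3.4.1 allows the denominator of risk-group CAP incidence to rest on an undefined group, UAD control subjects, that is not shown to represent catchment residents aged 60 and over

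*Protocol*

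**What the plan says.** Protocol 9.1 (Incidence assessment) makes risk-group rates conditional: "Where appropriate population-based denominators are available, incidence rates for at-risk and high-risk conditions will be generated". Protocol 12.4.2 repeats the condition: if population denominators for adults aged 60 and over "are available for underlying at-risk and high-risk medical conditions, incidence will be calculated specifically for these risk groups". The endpoint in Protocol section 8 has as its numerator "Number of CAP events identified by screening log multiplied by the proportion of CAP subjects with specific risk condition(s"), divided by the estimated number of residents aged 60 and over with the same condition.

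The SAP describes the source of that denominator in two ways.

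- SAP 2.2.3 says that local sources supply population counts for the surveillance area, including counts by risk condition. SAP 3.3.1 says of the population with the condition: "which will be obtained from local source(s) depending on availability".
- SAP 6.3.4.1 takes the risk share in the numerator from enrolled participants. It then builds the risk population from the "frequency of a given risk factor obtained from other sources (e.g., UAD control subjects or real-world data analyses"), multiplied by "denominator counts for that age group from local government sources". The analysis is to be done only if such data become available.

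The term UAD control appears in one other place, the carriage-replacement adjustment in SAP 6.1.1.2, and is not defined there either. The controls that are defined belong to the test-negative design. Protocol 9.1 says "Controls are hospitalised patients with pneumonia meeting the inclusion and exclusion criteria", and Protocol 12.1.1 and SAP 3.1 and 3.3.1 agree. Study UAD testing is described only for enrolled participants.

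**The concern.** The aim of this exploratory objective is to show CAP incidence in at-risk and high-risk adults. That needs the frequency of each condition among people who could become CAP patients, that is, residents aged 60 and over. A frequency taken from any other group carries its bias straight into the rate.

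SAP 6.3.4.1 names a group with no stated age range, area, recruitment or condition definitions. A programmer working only from these two documents would find one set of UAD-tested controls, the test-negative CAP patients. Using them would set the risk share of CAP patients against the risk share of mostly the same CAP patients, and the rate ratio would say little about risk. The closing condition on data availability would not prevent this, because the eCRF already holds those patients' risk conditions.

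**Working it through.** **Inputs**

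- CAP admissions per year, N = 1,800 (Protocol 12.1.2).
- Immunocompromised share of CAP admissions, p = 36% (Protocol 12.1.2 and Table 6, note d).
- Vaccine-type (case) share of CAP, v = 9%, varied from 7% to 13% (Protocol Table 6).
- Population aged 60 and over in the two municipalities, Pop = 103,844 (Protocol 9.1).
- General-population prevalence of high-risk conditions at age 60 and over, q: not in the documents. Assumed range 5% to 30%.

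**Step 1: the plan's own figures.** 1,800 × (1 − 0.36) = 1,152, against the stated ~1,150. 1,800 × 0.09 × 0.64 = 103.7, against the stated ~104. Both reproduce. The documents give no risk-group rate to check.

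**Step 2: the estimator.** Risk-group rate = (N × p) / (Pop × q). Overall rate = N / Pop = 1,800 / 103,844 = 1,733 per 100,000 per year. The ratio of the two is p / q, so everything depends on where q comes from.

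**Step 3: q from the test-negative CAP controls.** Treat enrolled CAP patients as cases (share v) plus controls (share 1 − v). Then p = v × p_case + (1 − v) × p_control. Setting q = p_control gives

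ratio = (1 − v) + v × (p_case / p_control).

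At v = 9%:

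| p_case / p_control | Ratio to overall rate | High-risk rate per 100,000 |
|---|---|---|
| 0.5 | 0.91 + 0.045 = 0.955 | 1,655 |
| 1 | 0.91 + 0.09 = 1.000 | 1,733 |
| 1.5 | 0.91 + 0.135 = 1.045 | 1,811 |
| 2 | 0.91 + 0.18 = 1.090 | 1,889 |

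For v from 7% to 13% and the same range of p_case / p_control, the ratio runs from 0.935 to 1.13. If the frequency is applied within age groups, as the SAP wording suggests, each risk-group rate collapses to its age-specific rate, and the pooled rate may differ somewhat from the overall rate.

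**Step 4: q from the general population (assumed).** N × p = 1,800 × 0.36 = 648 high-risk CAP admissions per year.

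| q (assumed) | Ratio 0.36 / q | High-risk rate per 100,000 |
|---|---|---|
| 5% | 7.2 | 12,480 |
| 10% | 3.6 | 6,240 |
| 20% | 1.8 | 3,120 |
| 30% | 1.2 | 2,080 |

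The two Table 3 counts that are given (35,106 + 46,802 = 81,908) raise the overall rate to 2,198 per 100,000 but leave every ratio unchanged.

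**Step 5: q from an outside UAD group.** The ratio is still p / q, but the documents say nothing about that group from which q could be judged. Neither the direction nor the size of any bias can be given.

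**The case against.** A reader might infer that every risk group's rate is bound to come out near the overall rate. The documents do not support that, for four reasons.

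- SAP 6.3.4.1 names enrolled participants as the numerator source and then turns to other sources for the frequency, listing UAD control subjects beside real-world data. That wording points away from the enrolled CAP patients.
- The availability condition fits the same reading: data already in the eCRF would not need to be made available. The documents also call their own controls test-negative controls, never UAD controls.
- The group is one of two examples, not the prescribed method. Real-world data may be chosen instead.
- A population count multiplied by a prevalence is a legitimate way to reach the estimated number of residents that Protocol section 8 asks for. The method itself is not a departure from the Protocol.

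It is also fair to say that the prevalence range is assumed, and that the analysis is exploratory, descriptive and conditional.

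All of this stands against the claim of certain collapse. It does not settle the source. A named example in an SAP is permission to use it, and on neither reading do the documents show this one to be population-based, as Protocol 9.1 and 12.4.2 require. Condition definitions matter too. SAP Appendix 2.4 defines chronic kidney disease by a glomerular filtration rate below 60 mL/min, for example, and nothing says that the outside frequency must use the same rule.

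**Conclusion.** The point holds as a defect in a named data source, not as a demonstrated bias. SAP 6.3.4.1 permits a denominator source that is undefined, differs from the local sources promised in SAP 2.2.3 and 3.3.1, and is not shown to meet the Protocol's condition.

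The near-cancellation in Step 3 applies only if the term is taken to mean the study's test-negative CAP controls. The contrast with ratios of 7.2 to 1.2 also rests on the Protocol's 36% and on the assumed 5% to 30% prevalence. A reader might go on to state a fixed percentage by which the planned rates are too low. The documents support no such figure, because it would need both that reading and a prevalence they do not give.

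The consequence is confined to the exploratory risk-group incidence objective. The text is still worth changing, because the less favourable reading would empty that objective of content and the correction is small.

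**What to change.** In SAP 6.3.4.1:

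1. Remove UAD control subjects as a source, and state that the study's CAP test-negative controls may not supply the risk-factor frequency.
2. Take the frequency by age band from general-population data for the catchment area or the Madrid Region, such as real-world data, with condition definitions matched to those used for the numerator.
3. Report no rate for a condition that lacks such a figure.

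This amends one SAP sentence, and no new data need be collected from participants. The downside is that some individual conditions may have no reportable rate, which Protocol 9.1 and 12.4.2 already foresee.

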4. AMENDMENTS AND UPDATES

Document History

Document	Version Date	Substantial or Administrative Amendment	Protocol section(s) changed	Rationale
Original protocol	26 May 2020			Not applicable
				(N/A)

B1851202 LOW-INTERVENTIONAL	STUDY	PROTOCOL
Version 3.0, 03 February 2022		

Amendment	13 April	Substantial	Protocol authors:	Changes in personnel
1	2021	amendment		responsible for the study
				Change of participating site: Hospital de Fuenlabrada is replaced by a new site, Hospital de Móstoles
			- Section 3: Update of version and authors and errata correction.	Updated timelines, taking into account the actual start date of the study.
			 Section 5: Update of study milestones dates. Section 6, 7, 8: errata 	
			correction.	

		data for the new participating site and update of population data for both sites.	Inclusion of new site with updated population data. Data are also updated with the available figures as of 2021 for the previous site, to homogenize the sources of information in the two participating sites.
		Inclusion criteria wording, modified to	Replacement of Hospital de Fuenlabrada with a new site, Hospital de Móstoles.
		-	Update to include COVID vaccination.
		- Section 10.3 and 10.4 Visit 2 and 3.	Detail cause of death.
		-Section 12.1.2. Erratum correction.	
			Updated reference for latest population figures.
Amendment 03	amendment		Changes in personnel responsible for the study.
		the principal investigators and sites participating in the study is updated.	Addition of one new participating site: Hospital Universitario Rey Juan Carlos de Móstoles in order to increase recruitment.
		- Section 3: Update of study version.	

PFIZER CONFIDENTIAL CT45-GSOP-RF152.0 Low-Interventional Study Protocol Template 05-Dec-2019 Page 15 of 70

	-Section 7. Rationale for Addition of RSV testing. the addition of Respiratory Syncytial Virus (RSV) testing.
	- Section 8: Update of exploratory objectives. Inclusion of new exploratory objective: RSV PCR testing in saliva samples collected for pneumococcal testing
	- Section 9: Update of Inclusion of new site. data for the new participating site.
	- Section 9.1.1: Deletion of inclusion criterion #4. Residents and non- residents of hospitals' geographical catchment area will be included to increase enrolment.
	-Section 10. Study It was repeated. procedures first paragraph deleted.
	-Section 10.2: Addition Control of confounding. of RSV vaccination history.

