10.3. Visit 1 Day 1 (Screening/Enrolment)

All relevant patients who are eligible via inclusion in the screening process will be offered enrolment to the consented study. The study would be explained by a healthcare professional who will also answer any questions the patient has before taking written informed consent to participate in the study. Once consent has been given, data and samples will be collected per the SCHEDULE OF ACTIVITIES in Section 6.

- If the patient meets all the inclusion criteria and none of the exclusion criteria, they will be informed of this study and asked for written informed consent (see Section 15.1).
- Once informed consent is obtained, a participant number will be assigned to the patient. The participant number will contain no initials or any other personal data that may identify the patient. Hospitalised participants that are recruited more than once as new cases (see Inclusion Criteria, Section 9.1.1) will be assigned a new participant number. Multiple events for a single participant will be linked in the electronic Case Report Form (eCRF) (for example, capturing prior study number(s) in the eCRF for the new event(s)).
- Collect Adverse Events (AEs) and Research Related Injury (RRI) as outlined in Section 16.
- Collection of urine for pneumococcal testing per Section 11.2.3.
- Collection of saliva sample at selected study sites per Section 11.2.4.

Specifically, at this visit the following data will be recorded in the eCRF:

PFIZER CONFIDENTIAL CT45-GSOP-RF152.0 Low-Interventional Study Protocol Template 05-Dec-2019 Page 35 of 70

- Date informed consent is obtained.
- Eligibility of the subject. It will be confirmed that the participant meets all inclusion criteria and no exclusion criteria to be eligible for the study.
- Demographic data: date of birth; sex, nationality, country of birth.
- Surveillance area resident: Do you live in the study catchment area? (yes/no).
- Residence setting (eg, nursing home, long-term care facility for those with disability or dependency, private residence, or other).
- Weekly exposure to children <5 years of age.
- Body Mass Index (BMI) (height and weight).
- Smoking status (current/previous/never).
- Alcohol/drug use.
- Vaccination history.
 - Pneumococcal, last date of administration for PCV13 and PPV23. PCV20 immunisation will also be collected once available in the region.
 - Influenza vaccination in last year, date of administration.

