12.1.3.5. Incidence CAP Population (Exploratory Analysis Population)

The calculation of incidence will include all CAP events identified on the screening log as residents of the hospitals' geographical catchment area either prospectively or retrospectively through ICD discharge code review.

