# 6.3.4. Exploratory Endpoint 4 - Incidence Rate of CAP cases with specific risk condition

The incidence rate of CAP residents with a specific risk conditions will be calculated using the number of CAP events, identified in the screening log, multiplied by the proportion of CAP population with specific risk condition(s), divided by the estimated number of persons ≥60 years in surveillance region with the same specific risk condition(s), in aggregate for at-risk and high-risk conditions and for individual risk groups.

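### Incidence is defined for catchment residents only, but the proportions that scale it to pneumococcal, radiologically confirmed and risk-group rates are not restricted to residents

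*Protocol*

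**What the plan says.** **Who counts towards incidence.** The incidence paragraph of Protocol 9.1 ends with the rule that non-residents of the hospitals' "geographic catchment area will be excluded from incidence estimations". Protocol 12.1.3.5 agrees: "The calculation of incidence will include all CAP events identified on the screening log as residents" of the catchment area. In Protocol 12.4.2 the numerator joins study subjects to other "unconsented patients captured on screening log as residents". SAP 4.4 limits both the enrolled and the unenrolled parts of its incidence population to residents, and SAP 5.2.4 does the same for numerator and denominator.

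**Who may be enrolled.** The three inclusion criteria in Protocol 9.1.1 contain no residence condition. The amendment table in Protocol 4 gives the reason: residents and non-residents of the "geographical catchment area will be included to increase enrolment".

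**Where the scaling proportions come from.**

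- Pneumococcal CAP (Protocol 12.4.2): "the proportion of CAP events among study subjects with pneumococcus identified by any means, will be multiplied by the calculated CAP incidence rate". The next sentence there treats radiologically confirmed CAP in the same way.
- Risk groups (Protocol 8): the screening-log count is multiplied by the proportion found in CAP subjects.
- Risk groups (SAP 6.3.4): the count is "multiplied by the proportion of CAP population with specific risk condition(s"). SAP 4.5 defines the CAP population as per-protocol subjects with a final CAP diagnosis and does not mention residence.
- Risk groups (SAP 6.3.4.1): the proportion among enrolled participants is used to fill in the risk-group count for unenrolled patients only.

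Residence is recorded yes/no for every enrolled subject (Protocol 10.3) and listed among the log fields (Protocol 10.2).

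**The concern.** Each scaled rate is a product of a residents-only CAP rate and a proportion drawn from a group that may include non-residents. The pneumococcal, imaging and risk profile of non-residents then enters rates from which the protocol says they are excluded. If non-residents admitted to these hospitals differ from residents on the characteristic in question, the reported rate does not describe the catchment population.

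No planned check would show this. The comparison of enrolled with unenrolled patients in SAP 6.3.1.1 covers age, sex, nationality, radiological confirmation and ICU status. It does not include residence.

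There is also a sign that the opening of enrolment was not carried through the SAP. SAP 4.4 still refers to inclusion criterion 4 for unenrolled patients, whereas the current inclusion criteria stop at 3.

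**Working it through.** The plan gives no pneumococcal, radiologically confirmed or risk-group incidence figure, no expected non-resident share, and no proportions split by residence. There is no stated figure to reproduce, so the check is algebraic, followed by an illustration.

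**Notation.** s = non-resident share of enrolled CAP subjects; p_r and p_n = the proportion of interest in residents and non-residents; k = p_n / p_r; u = share of resident CAP events that are unenrolled.

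**All events scaled** (Protocol 12.4.2 for pneumococcal and radiologically confirmed CAP; Protocol 8 and SAP 6.3.4 for risk groups). The proportion used is (1 − s)·p_r + s·p_n. Dividing by p_r gives

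ratio to the residents-only rate = 1 + s(k − 1).

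**Only unenrolled events scaled** (SAP 6.3.4.1). Enrolled residents are counted directly and the mixed proportion is applied to the rest. If enrolled and unenrolled residents share the same p_r,

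ratio = (1 − u) + u[1 + s(k − 1)] = 1 + u·s(k − 1).

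**Factor 1 + s(k − 1) over assumed values of s and k:**

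| s | k = 0.5 | k = 0.75 | k = 1 | k = 1.5 | k = 2 |
|---|---|---|---|---|---|
| 5% | 0.975 | 0.988 | 1 | 1.025 | 1.05 |
| 10% | 0.95 | 0.975 | 1 | 1.05 | 1.10 |
| 20% | 0.90 | 0.95 | 1 | 1.10 | 1.20 |
| 30% | 0.85 | 0.925 | 1 | 1.15 | 1.30 |

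**Illustration for the high-risk rate.** Protocol 12.1.2 expects 36% of CAP admissions to be immunocompromised. That figure is for admissions in general, so using it as p_r is an assumption. So are p_n = 25% to 55% and the values of s. For u, Table 6 and the text below it take 70% of CAP inpatients as enrolled, so u = 30%.

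- s = 10%: 0.9 × 0.36 + 0.1 × 0.25 = 0.349, and 0.9 × 0.36 + 0.1 × 0.55 = 0.379. Against 0.36 this is −3.1% to +5.3% with all events scaled. Multiplied by u = 0.3, it is −0.9% to +1.6%.
- s = 20%: 0.8 × 0.36 + 0.2 × 0.25 = 0.338, and 0.8 × 0.36 + 0.2 × 0.55 = 0.398. Against 0.36 this is −6.1% to +10.6% with all events scaled. Multiplied by 0.3, it is −1.8% to +3.2%.
- s = 20% with the 50% enrolment of Table 6 scenario 12 (u = 0.5): −3.1% to +5.3% under SAP 6.3.4.1.

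With the proportion taken from enrolled residents only, s = 0 and the ratio is 1 under either rule.

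**The case against.** **The general rule may already cover this.** The exclusion sentence closes the same Protocol 9.1 paragraph that introduces risk-group incidence, SAP 4.4 sets up a residents-only incidence population, and SAP 6.3.4 itself speaks of residents. A careful analyst could apply the filter throughout, and nothing in the documents says outright that non-residents enter the proportions. That much stands. But no rule for a proportion points to SAP 4.4, and SAP 6.3.4 names a different defined set. SAP 4.4 could not supply the pneumococcal or risk proportions unaltered either, because it includes unenrolled patients, for whom the log fields hold neither item. For pneumococcal CAP the SAP gives no formula, so the Protocol 12.4.2 wording is the only rule.

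**Full enrolment.** A reader might infer that the mismatch survives full enrolment for all three kinds of rate. The documents do not support that for risk groups. Under SAP 6.3.4.1 the proportion reaches only unenrolled patients, so with everyone enrolled nothing is scaled and the bias is zero. It would survive under Protocol 12.4.2, and under Protocol 8 and SAP 6.3.4 as worded.

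**Radiology.** The screening log lists radiological confirmation alongside residence (Protocol 10.2), and SAP 6.3.1 introduces these rates as obtained from the log. Confirmed CAP could therefore be counted directly in residents. This stands as a remedy, but Protocol 12.4.2 still prescribes multiplication.

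**Size.** SAP 5.2.4 says the hospitals serve a defined population, which gives no support for a large non-resident share. This also stands: s and k are unknown.

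**Conclusion.** The residence rule governs the CAP count and the denominator but is not written into the scaling proportions, and the text as it stands lets non-residents into them. The effect is the factor 1 + s(k − 1) for pneumococcal and radiologically confirmed CAP. For risk groups it is that factor or the smaller 1 + u·s(k − 1), because SAP 6.3.4 and 6.3.4.1 differ on which events are scaled.

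The illustrated −6% to +11%, or −1.8% to +3.2% under SAP 6.3.4.1 at 70% enrolled, rests on an assumed non-resident share of 20%, an assumed 25% to 55% in non-residents, and the use of 36% as the resident value. The true bias may be zero. The documents offer no inputs for an equivalent illustration of the pneumococcal or radiology multipliers.

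A reader should not infer that the basic CAP rate or vaccine effectiveness is compromised. The former is already limited to residents and the latter does not use these proportions. Only exploratory incidence endpoints are affected. The correction is still worth making, because it brings the rates into line with the protocol's own exclusion at almost no cost.

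**What to change.** - In Protocol 12.4.2 and SAP 6.3.1.1, 6.3.4 and 6.3.4.1, state that every proportion used to scale CAP incidence is computed in enrolled CAP participants recorded as surveillance-area residents. The proportion in all enrolled CAP participants can be kept as an optional sensitivity analysis.
- Align SAP 6.3.4 with 6.3.4.1 on whether the risk proportion scales all events or only unenrolled ones.
- Restrict the enrolled-versus-unenrolled comparison in SAP 6.3.1.1 to residents.
- Radiologically confirmed CAP may instead be counted directly among residents on the screening log.

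The cost is one filter on a variable already in the eCRF and the log, and slightly fewer subjects behind each proportion. No new data are needed.
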